- Patients: If patients submit an online consultation predicted by AI Triage as emergency at any time or urgent when their GP practice is closed, they immediately receive an automated 'signposting' message advising them to contact emergency services or the NHS 111 'out of hours' service, respectively (Appendix 1, Screenshot 3). They will also be presented with supporting advice from NHS.uk if relevant articles exist on the website. If their online consultation is predicted as 'routine', the patient may be presented with self-help advice from NHS.uk if relevant articles exist on the website (Appendix 1, Screenshot 4). Patients can accept this advice and cancel their online consultation, and the GP practice will not receive the form in their PATCHS inbox but can view it in a

Version 1.1 01/03/2024 IRAS ID: 331286

separate 'cancelled' folder if they wish. Alternatively, patients can ignore the advice and continue to submit their online consultation to their GP practice at their own risk.

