Limitations with the above approach include that: staff triage decisions could be applied by non-clinicians which could be systematically different to those applied by clinicians (43); we assume that patients who receive a signpost message and cancel their online consultation have not experienced a care delay; and the triage decisions made by GP practice staff may be highly variable. We will therefore conduct sensitivity analyses where: we restrict triage decisions to those only made by clinicians; we exclude patients who receive a signpost message and cancel their online consultation; we define online consultations as urgent and emergency in intervention and control practices if they are predicted as either 'urgent' or 'emergency' by Al Triage. We will also conduct sensitivity analyses where we sub-sample practices and patients with similar: baseline levels of the outcome measure, monthly volume of online consultations per 1000 patients, prevalence of urgent and emergency online consultations, agreement with AI Triage predictions, contributions to AI Triage model training, and other variables matched during randomisation and model adjustment where appropriate. Further sensitivity analyses may be undertaken based on findings from the process evaluation (44), for example, we may find a cohort of practices that did not engage with the Al Triage training, and we may test the hypothesis that Al Triage was less effective at reducing delays in urgent and emergency online consultations for them. We will also explore using an alternative analysis approach, interacting practice group with time and period to estimate the adjusted intervention time series. For example, a difference-in-difference method pooling the outcome (and the offset) in the preand intervention periods.

Health inequalities

We will use the pre-intervention period to assess for inequalities in the influence of patient characteristics on experiencing urgent and emergency care delays in both the pre- and intervention periods. We will use

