We will calculate the overall accuracy (proportion of 'correct' predictions), true positive rate, true negative rate, positive predictive value, and negative predictive value of AI Triage in intervention practices. Our primary measure of accuracy will be for urgent and emergency online consultations combined; secondary measures will assess urgent and emergency online consultations separately. There is no gold standard test to decide the 'correct' triage decision for online consultations written by patients in their own words. We will therefore use the triage decisions made by GP practice staff when processing online consultations and consider their triage decision as 'correct'. Where AI Triage predicts an online consultation as 'urgent' or 'emergency' we will consider it a:

- **True positive** if the triage decision is not changed by staff, or if staff change the triage decision and the highest triage decision applied by staff is 'urgent' or 'emergency'.
- False positive if staff change the triage decision and the highest triage decision applied by staff is
 'routine'.

Where AI Triage predicts an online consultation as 'routine', we will consider it a:

- **True negative** if the triage decision is not changed by staff, or if staff change the triage decision and the highest triage decision applied by staff is 'routine'.
- False negative if staff change the triage decision and the highest triage decision applied by staff is 'urgent' or 'emergency'.

We will quantify cases where emergency online consultations have been predicted as 'routine' as these represent the highest risk misclassifications. The Spectra Analytics Clinical Safety team will investigate these and other patient safety incidents reported by GP practices as per their internal processes to comply with MHRA and NHS DCB0129 standards (16). We will review their findings to understand if there are patient groups or online consultation topics that are at higher risk of misclassification by Al Triage.

Potential triage behaviour change in control GP practices

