We will obtain AI Triage predictions (urgent and emergency – both separate and combined) for control practices for each online consultation submitted during the intervention period and compare them to the actual triage decisions made by GP practice staff using the same definitions of true/false positives/negatives above. These predictions will differ from those in intervention GP practices because they will not have been presented to GP practice staff whilst they processed the online consultations. It identifies a group of patients for whom potentially different triage decisions would have been made if AI Triage had been enabled in those practices. We will then estimate the potential impact of these different triage decisions.

Observed triage behaviour change in intervention and control GP practices

To evaluate observed changes in triage behaviour, we will compare monthly and weekly time series counts of urgent and emergency triage decisions (both separate and combined) made by intervention and control GP practices. In intervention practices we will consider a triage decision as urgent or emergency if the highest triage applied by staff is 'urgent' or 'emergency' or an AI Triage prediction of urgent or emergency is left unchanged (same definition as 'true positives' above). In control practices, we will consider a triage decision as urgent or emergency if the highest triage applied by staff is 'urgent' or 'emergency'. We will also measure counts of patients cancelling their online consultations, and map whether patients cancel their request or receive input from a clinician following a signpost message and/or emergency prediction.

[figure not shown]
Sensitivity analyses

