Similar to the interrupted time series analysis, limitations with the above approach include that: staff triage decisions could be applied by non-clinicians; the true urgency of an online consultation may only be apparent when further information has been obtained from the patient (e.g. over the telephone); we assume AI Triage predictions for patients who receive a signpost message and cancel their online consultation is correct. We will therefore conduct sensitivity analyses where: we restrict triage decisions to those only made by clinicians; the final triage decision when the online consultation is resolved is used; patients who receive a signpost message and cancel their online consultation are excluded. As mentioned above, multiple online consultations from the same patient are expected to be infrequent, though will be assessed by using a patient-level variable in models and by re-running analyses after randomly sampling one online consultation per patient.

Health inequalities

We will assess the potential influence of AI Triage on health inequalities across different age groups, sexes, ethnic backgrounds, Index of Multiple Deprivation quintiles, and non-English language usage. In dose and reach metrics we will compare the proportion of each sub-group in the population using online consultations in intervention and control practices in the pre- and intervention periods (44), and to the characteristics of the wider practice populations in National General Practice Profiles (38).

Each accuracy metric will be tested for differences in performance between patient sub-groups. We will also undertake a failure case analysis to explore factors why AI Triage may have predicted incorrectly (46)

by comparing the characteristics of patients who have submitted online consultations classified as false positive and negatives to those of true positive and negative predictions ('error auditing') (47). Additional factors to test will include those related to the online consultation (including type of online consultation, time and day of submission), GP practice staff who applied the triage decision (including role, experience using PATCHS), and GP practice (including size, geographic location, experience using PATCHS).

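### Forms the AI calls routine and the patient cancels after self-help advice are scored as true negatives and drop out of the primary outcome, with no form-level analysis clearly aimed at them

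*Protocol*

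**What the plan says.** Protocol 7.2 (intervention practices, patients) describes two kinds of automated message. An emergency prediction at any time, or an urgent one when the practice is closed, triggers a signposting message towards emergency services or NHS 111. The other kind follows a routine prediction: "If their online consultation is predicted as 'routine', the patient may be presented with self-help advice from NHS.uk if relevant articles exist on the website". The consequence of acceptance is then stated: "Patients can accept this advice and cancel their online consultation, and the GP practice will not receive the form in their PATCHS inbox". The sentence goes on to allow staff to open the form in a separate folder for cancelled requests, at their discretion.

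Three later rules decide how such a form is counted.

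- **Accuracy (11.1, AI Triage accuracy in intervention practices).** A routine prediction is a true negative if staff leave it as it is. It becomes a false negative only if staff change it to urgent or emergency. On safety the section adds: "We will quantify cases where emergency online consultations have been predicted as 'routine' as these represent the highest risk misclassifications".
- **Primary outcome (section 9).** An intervention-arm form counts as urgent or emergency if staff give it that label, or if the AI gives it and staff leave it. The only stated assumption about cancelled forms concerns patients who received a signpost message.
- **Cancellation analyses (11.1).** The time series sensitivity analysis reads "we exclude patients who receive a signpost message and cancel their online consultation", and the process evaluation version reads "patients who receive a signpost message and cancel their online consultation are excluded". The behaviour-change analysis will "map whether patients cancel their request or receive input from a clinician following a signpost message and/or emergency prediction".

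**The concern.** The accuracy rules treat staff silence as agreement. That is reasonable for a form staff have processed. It is weak for one that never entered the inbox and that nobody was required to read. On the self-help route, an AI miss is scored as a correct prediction unless someone chooses to open the folder and relabel it.

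The protocol sees this problem for the signpost route: it states an assumption and tests it by exclusion. It does neither for the self-help route. The error favours the device. It also arises only where AI Triage runs, because the protocol describes no AI-triggered self-help message in control practices. What is at stake is the credibility of the intervention-arm accuracy table and of the safety count, and to a smaller and uncertain degree the primary outcome.

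**Working it through.** **Tracing one form.** Take a form that staff would have called urgent or emergency but that the AI predicts as routine. Self-help advice is shown, the patient cancels, and no one opens it.

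| Rule | Result for this form |
|---|---|
| Accuracy table (11.1) | True negative, since no staff change was made |
| Count of emergencies predicted routine (11.1) | Not counted, since that needs a staff label |
| Primary outcome (section 9) | In neither numerator nor denominator |
| Exclusion of signpost-and-cancel forms (11.1, both analyses) | Not clearly reached, since no signpost message was sent |
| Urgency redefined by AI prediction (11.1) | Still left out, since the AI said routine |
| Mapping of cancellations (11.1) | Not clearly reached: neither signpost message nor emergency prediction |

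**Inputs.**
- 20 intervention practices, 50 urgent and emergency forms a month, 12 months (11.2): 20 × 50 × 12 = 12,000 forms.
- True positive rate t: 84% in the test set and 94% in early adopter practices (section 5), taken here as true rates.
- Target: 25% to 20% delayed (11.2). The stated total of 2,928 reproduces: with a pooled two-sided test, [1.960·√(2×0.225×0.775) + 1.2816·√(0.25×0.75 + 0.20×0.80)]² / 0.05² rounds up to 1,464 per arm, and 2 × 1,464 = 2,928.
- Share c of AI misses cancelled after self-help advice: **not in the protocol**. A range of 5–20% is assumed.

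**Accuracy.** Misses = 12,000 × (1 − t), which is 1,920 at 84% and 720 at 94%. Hidden forms = misses × c. Apparent true positive rate = t / [t + (1 − t)(1 − c)].

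| t | c | Hidden forms | Apparent rate |
|---|---|---|---|
| 84% | 5% | 96 | 0.84/0.992 = 84.7% |
| 84% | 20% | 384 | 0.84/0.968 = 86.8% |
| 94% | 5% | 36 | 0.94/0.997 = 94.3% |
| 94% | 20% | 144 | 0.94/0.988 = 95.1% |

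The true negative rate and negative predictive value move less because routine forms are so numerous. With 6.5% of forms urgent or emergency (section 5), 12,000 such forms imply 12,000 × 0.935/0.065 ≈ 172,600 routine ones. Adding 384 hidden forms, and assuming a specificity of 50–90%, raises the true negative rate by about 0.02–0.11 points and the negative predictive value by about 0.24–0.44 points.

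**Primary outcome.** Let v be the hidden share of the 12,000 forms, p the observed delay proportion and q the delay proportion among hidden forms. The understatement is v(q − p).
- If q = p, it is zero.
- If every hidden form was in truth delayed (q = 1), it is v(1 − p). With v = 36/12,000 = 0.003 this is about 0.2 points. With v = 384/12,000 = 0.032 it is 0.032 × 0.75 = 2.4 points at p = 25%, or 0.032 × 0.80 ≈ 2.6 points at p = 20%.

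**The case against.** A reader might infer that these forms never reach staff and are invisible to every planned measure. The protocol does not support that. Staff can open cancelled forms. The proportion of consultations cancelled is a secondary outcome, and cancellations are also counted in the process evaluation, in neither case only after signposting. Emergency department attendances and emergency admissions are measured. AI predictions in control practices are compared with staff decisions made without seeing them, which estimates the miss rate free of this cancellation route. Practice-reported safety incidents are reviewed. All of this stands. But these measures are aggregate or indirect. The hospital data link by practice code only, and none of the measures corrects the intervention-arm accuracy table or safety count.

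It can also be said that an unprocessed form has no staff decision, so its handling is merely unspecified and belongs in the SAP. That has some force. However, the rule printed in the protocol, applied as written, makes the form a true negative.

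The term signpost might be meant broadly: the wider feature is called Signpost AI, and section 10 lists signposting messages without defining them. That is possible, but 7.2 describes self-help separately. Section 9's assumption that these patients sought care from other services also does not describe someone who accepted self-help.

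Finally, the size rests on an assumed share, and advice appears only where a relevant article exists. In control practices, too, urgent forms that staff do not flag leave the denominator; only the self-help route is specific to the intervention. Both points are correct and limit what can be claimed for the primary outcome.

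**Conclusion.** The point holds as a gap in the accuracy and safety measures. As the rules are written, AI misses cancelled after self-help advice are scored as correct predictions unless staff choose to relabel them. This biases the true positive rate upward (by 2.8 points at a true rate of 84%, or 1.1 points at 94%, if 20% of misses are cancelled), moves the other two metrics slightly, and makes the count of emergencies predicted as routine a minimum.

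The effect on the primary outcome is uncertain. The 2.4–2.6 point figure combines the higher miss rate, the top of an assumed cancellation range and delay in every hidden form; with equal delay rates there is no bias. A reader might conclude that the primary comparison is seriously distorted, or that these are the device's most harmful errors. The protocol has no data on the cancellation share or on harm after self-help cancellation, so neither conclusion is supported. The change should be made because it is cheap and the direction of the accuracy bias is known.

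**What to change.** 1. **Accuracy (11.1).** Do not score a form as a true negative when the AI predicted routine, self-help was shown, the patient cancelled and no staff triage decision exists. Report such forms as a separate category, by arm and period where the route exists, and state that the count of emergencies predicted as routine is a minimum.
2. **Sensitivity analyses and mapping (11.1).** Extend the signpost-and-cancel exclusions in both analyses, and the cancellation mapping, to self-help cancellations. Add a self-help-shown flag to the extract in section 10, before the identifier key is deleted.
3. **Resubmission, descriptive only.** Report how many of these patients submit again within 48 hours and receive a staff decision of urgent or emergency. Run this before the sampling of one form per patient. Keep it out of the main safety count, because a later urgent label may reflect worsening and not an AI error. Optionally, add a sensitivity analysis that starts the delay clock at the first, cancelled form.

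The cost is some wording, one data field and modest programming; the AI prediction, cancellation indicator, patient identifier and date-times are already listed in section 10. The downsides are slightly smaller accuracy denominators and some correct routine predictions set aside. Patients who seek care elsewhere are still missed.

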7.3 End of study

The study will end when the final intervention GP practice has used AI Triage for 12 months. Intervention GP practices will be able to continue using the AI Triage intervention after the study if they choose. All control GP practices will be offered the AI Triage intervention after the study has ended.

8) STUDY PARTICIPANTS

8.1 Inclusion Criteria:

GP practices

GP practices must meet both the following criteria to be eligible for the study:

- Currently actively using PATCHS without AI Triage
- Actively used PATCHS without AI Triage for at least 12 months

Patients

To minimise bias and generate real-world evidence, we will include data from all patients who use PATCHS in both intervention and control GP practices that have not opted out of sharing their anonymised data for research purposes with UoM. Patients can only use PATCHS if they are at least 16 years old, though carers can use PATCHS on behalf of patients under the age of 16 if they have guardianship or parental responsibility (as manually verified by the GP practice in PATCHS (29)).

Data

All data inputted by patients and GP practice staff will be included. There are no minimum requirements in terms of data quality or missingness. There are minimum character input requirements for patients before they can submit an online consultation in PATCHS.

8.2 Exclusion Criteria:

GP practices

GP practices who do not meet all inclusion criteria above.

Patients

Patients who have opted out of sharing their anonymised data for research purposes with UoM will be excluded.

Data

Not applicable.

8.3 Recruitment:

GP practices

A list of GP practices meeting the inclusion criteria in the form of Organisation Data Service codes (freely available online from NHS Digital (30)) will be produced by Spectra Analytics. This will be shared with the UoM research team who will use publicly available datasets from the Office for National Statistics and

NHS Digital to identify practices on the list that are representative of England in terms of patient population size (40), geographic region, and deprivation (34) to maximise generalisability and ensure our research is relevant to underserved groups in clinical research.

Intervention GP practices will be contacted by Spectra Analytics as they normally would in routine clinical practice using their standard 'onboarding' process for AI Triage described above. They are contacted by email which includes links to associated online help articles (25), optional eLearning modules based on these articles, and a Clinical Safety Case Report as per NHS clinical risk management standards for software (DCB0129 (16) and DCB0160 (26)). If no response is received from the GP practice within two weeks, a follow-up email is sent. One final email is sent one to two weeks later if still no response has been received. Control GP practices will be contacted at the end of the 12-month intervention period using the same 'onboarding' process as intervention GP practices.

To become intervention GP practices, practice managers must reply to emails from Spectra Analytics sent as part of the 'onboarding' process to confirm they consent to using Al Triage. When intervention and control GP practices start using PATCHS without Al and staff create user accounts, they are informed their anonymised data may be shared with UoM for research purposes.

GP practices and staff are not under any time pressure to decide whether they want to use PATCHS without AI in their practice. Intervention GP practices (and control practices at the end of the study period) will be given approximately one month to decide whether to use AI Triage.

Patients

Patients meeting the study inclusion criteria will be identified from the PATCHS database by Spectra Analytics. Patients will not be contacted by the UoM research team or Spectra Analytics.

[figure not shown]
When patients or their carers (verified by the GP practice (29)) use PATCHS they are informed their anonymised data may be shared with UoM for research purposes (Appendix 1, Screenshot 5). They can opt out of sharing their anonymised data at any point using a toggle button in the PATCHS system without affecting their ability to continue to use PATCHS to access GP services (Appendix 1, Screenshot 6).

Patients are not under any time pressure to decide whether they want to use PATCHS. They can also choose to not use PATCHS and contact their GP practice by telephone or in-person.

8.4 Randomisation:

GP practices will be randomly allocated to intervention (AI Triage now) or control (AI Triage later) groups in blocks of 5 practices in each arm (control and intervention) using the *runiform* command in Stata 18 with a target of 20 in each group. Depending on the response rate we may increase or decrease block size, and through a combination of randomisation and algorithmic approaches (31) using appropriate statistical software (32) we will attempt to match the two groups as closely as possible on patient population size (40), Index of Multiple Deprivation (34), monthly volume of online consultations per 1000 patients, baseline levels of the primary outcome measure, and baseline prevalence of urgent and emergency online consultations. We will also explore the possibility of matching GP practices on geographic region, rurality (36), number of whole-time equivalent GPs per 1000 patients (39), mix of patient ethnicities, and levels of patient morbidity (40), though given the target sample size is relatively small this may not be possible. Where we cannot match characteristics, we will attempt to adjust for them in our statistical models.

This is a single-blind study. The UoM research team will not know which GP practices are allocated to intervention or control groups. Due to the nature of the intervention GP practices cannot be blinded. The

UoM research team will randomly allocate GP practices to "0" or "1" groups using the approach described above. The allocation sequence will be provided to Spectra Analytics who will use statistical software to randomly allocate "0" or "1" to be the intervention group. They will then approach GP practices in the intervention group to offer them AI Triage as described elsewhere. Spectra Analytics will retain the mapping key and not share it with the UoM research team until after data analysis is finalised. The interrupted time series analysis (including analysis of the primary outcome measure) will not be undertaken until the end of the intervention period. Analyses will be undertaken by the UoM research team only not Spectra Analytics.

8.5 Participants who withdraw consent or lose capacity to consent:

If a patient opts out of sharing their anonymised data for research purposes with UoM (Appendix 1, Screenshot 6), we will withdraw their data. When a patient has used PATCHS it is impractical to find out whether they subsequently lose capacity as all registered patients at the GP practices can use PATCHS. If a GP practice staff member uses PATCHS then subsequently loses capacity, we will continue to use the data they provided before losing capacity. If data have already been extracted, we will be unable to withdraw participants' data because the data will have been anonymised and we will be unable to identify the participant.

9) OUTCOME MEASURES

Primary outcome measure

Our primary outcome measure is the proportion of delays in completing urgent and emergency online consultations at the patient-level:

(delayed urgent online consultations + delayed emergency online consultations)

- ÷ (total urgent patient online consultations
- + total emergency online consultations)

It was chosen because patients and clinicians we consulted during our PPI work felt it was the most clinically important outcome measure. Delays will be measured by the difference between the date-time that an urgent or emergency online consultation was submitted by a patient in PATCHS and the date-time the consultation was completed in PATCHS by GP practice staff. Based on our PPI work, we will consider an urgent online consultation delayed if it is not completed within 48 hours and an emergency online consultation delayed if it is not completed within 24 hours. Online consultations that have not yet been completed but were submitted by patients more than 48 hours previously at the point of data extraction will be included. In intervention practices we define online consultations as urgent or emergency where a GP practice staff member has applied a triage decision as either 'urgent' or 'emergency', or where AI Triage predicts an online consultation as 'urgent' or 'emergency' which is unchanged by staff. We will assume that patients who receive a signpost message and cancel their online consultation will have sought care from other services and not experienced a care delay. In control practices we define online consultations as urgent and emergency only if GP practice staff apply a triage decision as either 'urgent' or 'emergency'.

Secondary outcome measures

Interrupted Time Series Analysis

Patient-level - binary

 Proportion of delayed emergency online consultations at the patient-level (disaggregated primary outcome measure; denominator=number of emergency online consultations)

- Proportion of delayed urgent online consultations at the patient-level (disaggregated primary outcome measure; denominator=number of urgent online consultations)
- Proportion of online consultations cancelled by patients at the patient-level (denominator=number of online consultations)
- Proportion of online consultations assigned to clinicians (denominator=total number of online consultations)

Patient-level – continuous

- Absolute time to completion for urgent and emergency online consultations (combined and separate)
- Absolute time to completion for routine online consultations
- Absolute time to first staff user action in online consultation system for urgent and emergency online consultations (combined and separate)
- Absolute time to first staff user action in online consultation system for routine online consultations

GP practice-level – counts (workload measures)

- Proportion of total appointments provided by GP practices (denominator=GP practice population size
 (1))
- Proportion of online consultations submitted by patients (denominator= GP practice population size)
- Proportion of patients with emergency department attendances (denominator=GP practice population size (37))
- Proportion of online consultations with emergency department attendances (denominator=total number of online consultations (37))
- Proportion of patients with emergency hospital admissions (denominator=GP practice population size (37))
- Proportion of online consultations with emergency hospital admissions (denominator=total number of online consultations (37))

GP practice-level – continuous (cost measures)

- Cost of clinicians processing online consultations within the GP practice per 1000 patients
- Cost of emergency department attendances and emergency hospital admissions per 1000 patients

Quantitative process evaluation

For readability, these are described in more detail in the statistical analysis section.

- Fidelity, dose, and reach of Al Triage and online consultations
- Al Triage accuracy, true positive rate, true negative rate, positive predictive value, and negative
 predictive value for predicting urgent and emergency online consultations (combined and separate)
 in intervention GP practices
- Potential triage behaviour change in control GP practices
- Observed triage behaviour change in intervention and control GP practices

10) DATA COLLECTION, SOURCE DATA, AND CONFIDENTIALITY

Patient-level data

We will use anonymised routinely collected PATCHS data held by Spectra Analytics. Data are collected automatically each time both patients and staff interact with PATCHS. This includes data collected 'passively', including when users visit certain pages within the system, in addition to data collected intentionally inputted into the system such as triage decisions made by staff or when patients enter their

age, sex, and ethnicity. Each patient will be assigned a randomly generated identification number in the PATCHS database before sharing with the UoM research team. The mapping key will then be deleted using hard drive eraser software to anonymise the data. The following anonymised patient-level data will be shared by Spectra Analytics with the UoM research team:

- Patient randomly generated identification number
- Patient year of birth
- Patient sex
- Patient ethnicity according to methods mandated for NHS organisations and response codes set out in the NHS data dictionary (33)
- GP practice Organisation Data Service code (30)
- Index of Multiple Deprivation (34)
- Date-time online consultation was submitted by the patient
- Date-time online consultation was completed by GP practice staff
- Whether online consultation was submitted by patient or someone else (carer or staff member)
- Type of online consultation chosen by patient e.g. health problem or administrative request
- Whether the patient submitted their online consultation in a non-English language
- Triage predictions made by AI Triage regarding the online consultation
- Triage decisions made by GP practice staff regarding the online consultation
- Signposting messages presented to patient
- Whether the patient or carer cancelled the online consultation
- How the online consultation was processed by GP practice staff e.g. if it was assigned to other staff users in PATCHS, if messages were sent to the patient in response
- Role of staff who processed the online consultation e.g. GP, nurse, receptionist

A formal risk assessment by Spectra Analytics based on guidance from the Information Commissioner's Office (35) concludes there is a low risk of individuals being identified from the data through 'singling out', 'data linkages', or 'inference', and the data are therefore effectively anonymised (Appendix 2).

GP practice-level data

In addition to PATCHS data, we will also use the following GP practice-level data that we will link to PATCHS data via the GP practice Organisation Data Service (30) code:

- Built Up Areas from the Office for National Statistics (freely available online) (36)
- Emergency Care Dataset from NHS Digital Data Access Request Service (application required and cost associated) (37)
- National General Practice Profiles from Public Health England (freely available online) (38)
- GP Practice Workforce from NHS Digital (freely available online) (39)
- Total appointment counts from NHS Digital (freely available online) (1)
- Index of Multiple Deprivation from Office for National Statistics (freely available online) (34)
- Quality and Outcomes Framework performance from NHS Digital (freely available online) (40)

Data transfer and storage

Data sharing agreements will be signed between UoM and Spectra Analytics, and UoM and NHS Digital. Data will be transferred from Spectra Analytics and NHS Digital to UoM as password-protected comma separated value files using industry standard Hypertext Transfer Protocol Secure over a Transport Layer Security connection encrypted both in transit and at rest.

Once transferred to UoM, data will be stored on secure UoM Research Data Storage servers (41). These servers are only accessible by specific UoM users on the UoM network via multi-factor authentication. Only members of the UoM research team will be given permissions to access the data.

Data for the interrupted time series analysis (including the primary and secondary outcome measures – section 9) will not be transferred from Spectra Analytics and NHS Digital to UoM until after the intervention period has finished. Data for the quantitative process evaluation (section 9) will be transferred monthly from Spectra Analytics to UoM after GP practice recruitment has finished.

11) STATISTICAL CONSIDERATIONS

